9.2.4. Treatment Given as a Result of the Event

The event impact in terms of treatment provided will be as either: none, medication administered, non-drug therapy administered, surgery performed, hospitalization, or other (with a specification).

9.2.5. Outcome Assessment

The outcome of the event will be assessed as either: resolved, resolved with sequelae, ongoing, or death. Only one AE per subject is allowed to have an outcome assessment as “death.” If there are multiple causes of death for a given subject, only the primary cause of death will have an outcome of death.

9.2.6. Injection-site reactions

Injection-site reactions thought to be directly related to the injection are considered to be AEs of special interest, and will be assessed as per CTCAE v5.0.

For subjects who develop Grade 1 or Grade 2 events, therapy will be continued as per protocol. If a subject chooses to discontinue study treatment, the site should notify the protocol team leadership, and encourage the subject to complete any remaining study visits until the toxicity resolves.

For subjects who develop Grade 3 events following study drug injection, the subject should be reevaluated closely until the AE returns to Grade 1 or less, at which time study treatment may be reintroduced at the discretion of the site investigator. If the same Grade 3 AE recurs following the next administration of study drug, study treatment must be permanently discontinued. Subjects experiencing Grade 3 AEs requiring permanent discontinuation of study treatment should be followed closely for resolution of the AE to Grade 1 or less and the team leadership must be notified.

For Grade 4 events permanently discontinue therapy.

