3 STUDY DESIGN

This is a Phase Ib/II, multicenter study with a planned enrollment of up to 18 subjects in the Phase Ib portion of the study and 30 subjects in the Phase II portion of the study. The target population for this study is subjects with histologically confirmed diagnosis of CCR5 positive, metastatic triple-negative breast cancer (documented as having HER-2 negative, ER<1%, PR<1% disease) who are naïve to chemotherapy in metastatic setting (first-line) OR have failed first-line combination of chemotherapy and checkpoint inhibitor in metastatic setting (excluding carboplatin). A study flow schematic is presented in [Figure 3-1](#).

Figure 3-1: Study Schematic

Note: 1 treatment cycle = 21 (± 3) days

Note: Scans to be done at the end of 2 cycles (prior to Cycle 3) for the first 12 months and at the end of every 3 cycles (9 weeks) thereafter and at EOT, by CT, PET/CT, or MRI with contrast.

Phase Ib

Phase Ib is a dose escalation phase with 3 dose levels (cohorts) of leronlimab (PRO 140) administered in combination with a fixed dose of carboplatin at AUC 5. This dose finding portion of study will follow a “3+3” designed to determine the maximum tolerated dose (MTD) of leronlimab (PRO 140) administered as subcutaneous injection in subjects with histologically confirmed mTNBC that express CCR5. The MTD is defined as 1 dose level (cohort) below the dose in which dose limiting toxicities (DLTs) were observed in $\geq 33\%$ of the participants.

[figure not shown]
The calculation of the sample size for the Phase Ib trial is based on the traditional 3 + 3 dose escalation scheme which is conducted as follows:

- Subjects are treated in cohorts of three each receiving the same dose. For the assessment of a DLT subjects are observed for 3 weeks (Cycle 1) after the first application of the study treatment.
- If none of the three subjects of a cohort exhibits a DLT, the next cohort of three subjects receives the next higher dose.
- Otherwise, if at least one subject of a cohort exhibits a DLT, a further cohort of three subjects is treated at the same dose level (cohort) without escalating the dose.
- If exactly one out of the six subjects treated at this dose exhibits a DLT, the trial continues as planned at the next higher dose level (cohort).

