6.1.5. Leronlimab (PRO 140) - Dose Modifications

The dose interruption, reduction, and permanent discontinuation for any toxicity are described below.

Dose interruption: Refer to [Table 6-3](#) below. Recovery to acceptable levels must occur to allow leronlimab (PRO 140) continuation. Any adverse event deemed to be related to leronlimab (PRO 140) that requires a dose hold of more than 21 days will result in permanent discontinuation of leronlimab (PRO 140).

Table 6-3: Leronlimab (PRO 140) Dose Modification and Management for Injection Site Reactions

CTCAE Grade	Treatment Modifications
Grade 1	No dose adjustment is required.
Grade 2	First Occurrence: No dose adjustment is required. Second Occurrence of the same event: Closely follow-up for resolution of the AE to Grade ≤ 1
Grade 3	Withhold treatment until symptoms resolve to: • Grade 1 or less
Grade 4	Study treatment will be permanently discontinued
Dose Limiting Toxicities (DLT) as outlined under Section 3 (Study Design)	Study treatment will be permanently discontinued

Note:

- *If Grade 3 event meets the DLT criteria: Study treatment will be permanently discontinued*
- *If Grade 3 event does not meet the DLT criteria: Study treatment will be withheld until symptoms resolve to Grade 1 or less before administering the next dose.*

Dose Modification: If a dose-response relationship for toxicity is observed, a reduced dose can be given to the subject. Dose adjustments will be allowed based on the toxicity, efficacy evaluation, and clinical judgment by physician.

- **Cohort B (PRO 140 525 mg):**

Dose de-escalation: If a dose-response relationship for toxicity is observed at leronlimab (PRO 140) 525 mg dose, the dose can be de-escalated to 350 mg. If no toxicity is observed at reduced dose (350 mg), the subjects will receive the reduced dose until disease progression, consent withdraw or death. No more dose de-escalation will be allowed if another toxicity event is observed at reduced dose level.

- **Cohort C (PRO 140 700 mg):**

Dose de-escalation: If a dose-response relationship for toxicity is observed at leronlimab (PRO 140) 700 mg dose, the dose can be de-escalated to 525 mg. If no toxicity is observed at reduced dose (525 mg), the subjects will receive the reduced dose until disease progression, consent withdraw or death. One more dose de-escalation (to 350 mg) will be allowed as per discretion of the treating physician.

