7.10 TOXICITY ASSESSMENT

Any subject who receives at least one dose of study therapy will be evaluable for toxicity endpoints. Each subject will be assessed for the development of toxicity according to the timeframe referenced in the Schedule of Events table. Toxicity will be assessed according to CTCAE v 5.0 criteria. Refer to [Section 3](#) for the assessment criteria for dose limiting toxicity under Phase Ib of the study. Also

refer to [Table 6-3](#) and [Table 6-4](#) for the dose modification and management of leronlimab (PRO 140) and carboplatin for any toxicity.

All subjects will be followed for adverse events for 30 days after last dose of leronlimab (PRO 140) and carboplatin, or until the subject starts a new treatment, whichever occurs first.

Subjects who discontinue treatment for unacceptable adverse event(s) will be followed until resolution or stabilization of the adverse event (i.e. the grade is not changing). If a subject stops treatment due to unacceptable adverse event(s) but has not demonstrated disease progression, then the subject will be followed with imaging studies every 9 weeks until the time of progression radiographically according to RECIST v1.1 criteria.

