7.13 POST-INJECTION EVALUATION AND INJECTION SITE REACTION ASSESSMENT

At each treatment visit, an injection site reaction assessment will be made for the current and previous injection sites. Injection site reaction assessments are recorded by the Investigator starting after the first injection is given. Subject will be observed at approximately 30 minutes post-injection

[figure not shown]
or longer if necessary for injection site reaction as per CTCAE v5.0. Refer to [Sections 9.2.6](#) for more details.

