8.5 INTERIM ANALYSIS

No interim analysis (IA) will be performed for efficacy. There will be a safety review, once all three (or six) subjects from each cohort complete the DLT evaluation period (defined as cycle 1 or the first 21 days of treatment).

The Sponsor's Medical Monitor, CRO Medical Monitor and study investigators must be satisfied with data obtained in Cohort A before allowing subsequent enrollment of Cohort B. Likewise, they must be satisfied with data obtained in Cohort B before allowing subsequent enrollment in Cohort C.

In addition, should any of the following events occur in any cohort during the DLT evaluation period, the Data Safety Monitoring Board (DSMB) will meet to review available study data and make a final decision for dose escalation to the next cohort:

- a. Death in any subject in which the cause of death is judged to be possibly, probably or definitely related to leronlimab (PRO 140)
- b. The occurrence in any subject of an anaphylactic reaction to leronlimab (PRO 140)
- c. The occurrence in any subject of a severe local injection site reaction (Grade 3 which is not resolved or recurs; or Grade 4) that precludes administration of consecutive leronlimab (PRO 140) doses.
- d. The occurrence in any subject of a life-threatening SAE whose causal relationship to leronlimab (PRO 140) is judged to be probable or definite
- e. The occurrence of one or more non-life-threatening SAEs whose causal relationship to leronlimab (PRO 140) is judged to be definite
- f. The occurrence, in one or more subjects, of Grade 4 laboratory abnormalities, judged to be probably or definitely related to receipt of leronlimab (PRO 140)
- g. The occurrence of hematologic and non-hematological adverse events, judged to be possibly, probably or definitely related to receipt of leronlimab (PRO 140) based on previous clinical experience and that are of CTCAE Grade 3 or greater severity. Permissible exceptions to this rule include Grade 3 fatigue of less than one week duration, and Grade 3 nausea, vomiting, and diarrhea that resolve within 48 hours following institution of appropriate supportive care.
- h. Hy's law
- i. Neutropenic fever
- j. Grade 4+ neutropenia or thrombocytopenia >7 days
- k. Grade 3+ thrombocytopenia with bleeding

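### Table 6-3 and Section 9.2.6 of the protocol are not aligned on what to do when a Grade 3 injection-site reaction recurs

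*Protocol*

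**What the plan says.** Protocol Section 9.2.6 deals with injection-site reactions as adverse events of special interest. After a first Grade 3 reaction it lets the site investigator restart treatment once the reaction has fallen to Grade 1 or less. It then adds: "If the same Grade 3 AE recurs following the next administration of study drug, study treatment must be permanently discontinued". No cycle or phase is named.

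Table 6-3 in Section 6.1.5 is the leronlimab dose-modification table for the same reactions.

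- At Grade 2 it has a line for a repeat event, which opens "Second Occurrence of the same event: Closely follow-up for resolution of the AE to Grade". At Grade 3 there is no such line; the row holds treatment until Grade 1 or less.
- The note splits Grade 3 events in two. Those that meet the DLT criteria stop treatment permanently. For the rest, "Study treatment will be withheld until symptoms resolve to Grade 1 or less before administering the next dose".
- A separate DLT row also stops treatment permanently and refers to the Section 3 list. Criterion (c) of that list covers a Grade 3 local reaction that fails to resolve or comes back, provided that it prevents consecutive leronlimab doses.

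Section 7.10 sends sites to Table 6-3 for dose modification. Section 7.13 sends them to Section 9.2.6 for injection-site reactions. Neither Table 6-3 nor Section 9.2.6 mentions the other.

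**The concern.** A site that doses from the table could give another injection to a patient whom Section 9.2.6 requires to stop. What is at stake is re-exposure after a repeated severe local reaction. From Cycle 2 the Day 8 and Day 15 injections may be given by the patient at home, and footnote 19 of Table 4-1 says that the investigator's injection-site assessment does not apply to those doses. A clear stopping rule is most useful in that setting.

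**Working it through.** No sample size, power or event count is involved, so the check is a comparison of texts. The inputs are Section 9.2.6, Table 6-3 with its note, Section 3 criterion (c), and the statements on when DLTs are assessed.

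**When the DLT criteria apply.** Section 3 says: "For the assessment of a DLT subjects are observed for 3 weeks (Cycle 1) after the first application of the study treatment". Section 8.5 has cohorts reviewed once subjects "complete the DLT evaluation period (defined as cycle 1 or the first 21 days of treatment"). Section 7.10 points to Section 3 "for the assessment criteria for dose limiting toxicity under Phase Ib of the study". These support reading a DLT as something that can occur only in Phase Ib Cycle 1. However, they define the window for escalation decisions and the place where the criteria are found. Table 6-3 itself carries no cycle or phase limit. Both readings are therefore open:

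- Reading A: the Section 3 list applies as a set of event criteria at any time.
- Reading B: it applies only in Phase Ib Cycle 1.

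**The four cases for the same Grade 3 reaction recurring after the next dose.**

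| Recurrence | Section 9.2.6 | Table 6-3, reading A | Table 6-3, reading B |
|---|---|---|---|
| Phase Ib Cycle 1, prevents consecutive doses | Stop | Stop | Stop |
| Phase Ib Cycle 1, clears before the next weekly dose | Stop | Hold, then dose | Hold, then dose |
| Phase Ib from Cycle 2, or Phase II, prevents consecutive doses | Stop | Stop | Hold, then dose |
| Phase Ib from Cycle 2, or Phase II, clears before the next weekly dose | Stop | Hold, then dose | Hold, then dose |

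Rows 2 and 4 differ from Section 9.2.6 on either reading, because a reaction that has cleared in time can miss the condition in criterion (c) about consecutive doses. Row 3 differs only on reading B. Row 1 agrees throughout.

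Section 6.1.5 also stops leronlimab when a related event needs a hold of more than 21 days. That rule does not reach a recurrence that clears sooner.

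**Dosing outside the window on reading B.** Leronlimab is given on Days 1, 8 and 15 of each cycle, so the window covers 3 doses per Phase Ib patient and none in Phase II. All later Phase Ib dosing (up to 18 patients) and all Phase II dosing (30 patients) lie outside it. This counts exposure, not risk.

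**Criterion used.** The table assumes that criterion (c) governs injection-site reactions. Criterion (g) covers leronlimab-related non-hematological events of Grade 3 or more, and its exceptions do not include these reactions. If (g) were applied, Table 6-3 could require a stop at the first Grade 3 reaction, whereas Section 9.2.6 allows a restart. The two places would then disagree in the other direction.

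**The case against.** A reader who sees only the Grade 3 row might infer that Table 6-3 has no recurrence rule at all. The documents do not support that. The first bullet of the note and the DLT row stop treatment for events that meet criterion (c), and criterion (c) names recurrence. On reading A, a reaction still at Grade 3 when the next weekly injection is due prevents that injection, so the table stops treatment as Section 9.2.6 does. What then remains is the narrow case of a reaction that recurs and clears each time within the week.

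A reader might also infer that the two texts contradict each other outright, or that the table directs sites to re-dose after a recurrence. That goes too far. For a first Grade 3 reaction they agree on the condition for resuming. Beyond that the table sets a minimum condition for the next dose, and Section 9.2.6 adds a stop. A site can follow them in order: hold, restart, stop on recurrence. Section 7.13, which governs assessment at each treatment visit, leads to that stop.

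These arguments narrow the point but do not remove it. No text says that Section 9.2.6 prevails over the table, the table does not say which reading of the DLT row is meant, and rows 2 and 4 remain on both readings.

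**Conclusion.** The point holds as a minor internal inconsistency in the protocol, not as a design choice. The mismatch is firm for a recurrent Grade 3 reaction that clears before the next weekly dose, taking criterion (c) as the governing one. It widens to every recurrence from Phase Ib Cycle 2 and in Phase II only if the DLT criteria lapse after Phase Ib Cycle 1; Sections 3, 7.10 and 8.5 support that reading, but Table 6-3 does not state it.

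The documents give no rate of recurrent Grade 3 reactions, so no probability is claimed. Few patients are likely to be affected. Reactions were mostly mild in study 1102 and mild in study 2101 (Sections 1.4.5 and 1.4.9), and in CD03 they were neither more frequent nor more severe at higher doses (Section 1.4.14). Neither the sample size nor any planned efficacy analysis changes.

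**What to change.** In Table 6-3, split the Grade 3 row and the matching note into two lines:

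- *First occurrence, not a DLT:* withhold until Grade 1 or less.
- *Same Grade 3 reaction recurs after the next administration:* permanently discontinue study treatment, any cycle, either phase (see 9.2.6).

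Also state whether the DLT row applies outside Phase Ib Cycle 1. The cost is one table row, its note, one cross-reference and one clarifying sentence in the protocol. No new data or visits are needed.

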9.3 SERIOUS ADVERSE EVENTS

[figure not shown]
A SAE is defined as any AE that:

- Results in death
- Is life threatening (the subject is at immediate risk of dying from the adverse experience)
- Requires subject hospitalization or prolongs existing hospitalization
- Results in persistent or significant disability/incapacity
- Is a congenital anomaly/birth defect

- Important medical events that may not result in death, be life-threatening, or require hospitalization may be considered a serious adverse device effect when, based upon appropriate medical judgment, they may jeopardize the subject and may require medical or surgical intervention to prevent one of the outcomes listed in this definition

9.4 REPORTING OF SERIOUS ADVERSE EVENTS

The Investigator is required to report all SAEs that occur during the time period specified in [Section 9.2](#). Once the Investigator becomes aware of an SAE, he/she must report the SAE to Amarex Safety and Pharmacovigilance Department within 24 hours:

A written SAE report must include a full description of the event as described in [Section 9.2](#) and must follow within 24 hours from the time the Investigator first learned of the event. The Amarex Medical Monitor may request additional supporting documentation as it becomes available, such as lab reports, electrocardiogram [ECG] reports, discharge summary, hospital notes, etc, if applicable.

The Investigator is also responsible for reporting all SAEs to the appropriate Institutional Review Board (IRB) in accordance with local laws and regulations. The Investigator is responsible for maintaining documentation in the study file that indicates the IRB has been properly notified.

9.5 SAE FOLLOW-UP

All subjects experiencing an SAE, including the discontinued subjects, must be closely followed until sufficient information is obtained to indicate a return to normal status or until the event stabilizes at a level acceptable to the investigator (i.e., recovery, return to baseline status, no further improvement expected, or death).

For each SAE indicated as an unresolved event on the initial report, regardless of whether the subject completed the study or withdrew, the site should submit a follow-up report with updated information.

10 DIRECT ACCESS TO SOURCE DATA/DOCUMENTATION

Subjects will be identified on eCRFs by a unique subject identification number and on source documents by name and date of birth. No personal identifier will be used in any publication or communication used to support this research study. The subject identification number will be used if it becomes necessary to identify data specific to a single subject.

The local IRB, FDA, the monitors, auditors and personnel authorized by the Sponsor are eligible to review the medical and research records related to this study as part of their responsibility to protect human subjects in clinical research. They will be given direct access to source data and documentation (e.g., medical charts/records, printouts etc.) for source data verification, provided that subject confidentiality is maintained in accordance with local requirements. Access to electronic medical records may be governed by institution policy and each site will be required to ensure access while remaining compliant with institutional requirements.

11 QUALITY CONTROL AND QUALITY ASSURANCE

11.1 MONITORING REQUIREMENTS

The specific obligations outlined in 21 Code of Federal Regulations (CFR) and ICH guidelines require the Sponsor to maintain current personal knowledge of the progress of a study. Therefore, the Sponsor's designated monitor will visit the site during the study as well as maintain frequent telephone and written communication. The Investigator will permit the Sponsor to monitor the study as frequently as is deemed necessary and provide access to medical records to ensure that data are being recorded adequately, that data are verifiable and that protocol adherence is satisfactory.

As delineated above, the Investigator will permit representatives of the Sponsor and/or designated CRO to inspect all CRFs and corresponding study subject original medical records (source documents) at regular intervals throughout the study. Subject original medical records and other relevant data must be available to support all data recorded in the eCRF. In addition to the original medical records, these data may include but are not limited to study, laboratory reports, etc.

In accordance with federal regulations, site inspections will serve to verify strict adherence to the protocol and the accuracy of the data that is being entered on the case report forms. A Monitoring Log will be maintained at each study site. The Monitoring Log will be signed by the monitor, dated and stated the type of visit. The Investigator should be aware that the study site and subject records may be inspected by the Sponsor and or representatives of the designated CRO, FDA or other regional regulatory authority.

11.2 ACCEPTABILITY OF CASE REPORT FORMS (CRFs)

For each subject who has signed an informed consent form, a CRF must be completed. For subjects who are screen failures, this would be limited to the screen failure CRF page. All source documents and CRFs will be completed as soon as possible after the subject's visit and corrections to data on the CRFs will be documented, if applicable. The Investigator will review the CRFs to indicate that, to his/her knowledge, they are complete and accurate. CRFs will be reviewed by the Sponsor's or designated CRO's monitor, who will make a decision as to their acceptability.

11.3 MODIFICATION OF PROTOCOL

The Investigator will not modify or alter this protocol without first obtaining the concurrence of the Sponsor. Approval by the Investigator's IRB must also be obtained prior to implementation of the change, with two exceptions:

1. When necessary to eliminate apparent immediate hazard to the subject; or

- When the modification does not involve the subject's participation in the trial.

An amendment may also require modification of the informed consent form. The Investigator will provide an approval letter for the amendment and revised informed consent form, if applicable, to the Sponsor. An amendment must be provided in writing and it must be dated by both the Sponsor and the Investigator. If necessary, the Sponsor will submit protocol amendments to FDA and other appropriate regulatory authorities and notify other Investigators using this protocol.

